Aim 3: To explore the relationships between mGluR5 availability and functional network activity during initial abstinence in individuals with CUD. We will perform multi-modal analysis of PET and fMRI data to examine links between molecular and functional systems in CUD using emerging 'fusion' approaches. While exploratory in nature, we expect to find links between alterations in mGluR5 systems and functional reorganization in CUD (e.g., greater dorsostriatal mGluR5 may be linked to blunted frontoparietal inhibition).

Aim 4: To explore the relationships between mGluR5 availability, functional network activity (and their linkages) with cocaine self-administration (collected in some subjects during a prior version of this protocol), disease severity and chronicity, and psychometric assessments of impulsivity and compulsivity. While exploratory in nature, we expect more substantial neurofunctional alterations during initial abstinence will be associated with greater cocaine self-administration, disease severity, impulsivity and compulsivity in individuals with CUD.

Aim 5 (pilot): To assess the degree to which mGluR5 availability and functional network activity may change during early abstinence in CUD. A pilot sample of CUD participants (up to 10) will be invited to repeat [¹⁸F]FPEB PET and fMRI procedures within three weeks of initial scans (typically 5-14 days). A pilot sample of HC individuals (up to 10) will also be recruited to complete longitudinal MRI scanning procedures (i.e., two MRI scans up to 30 days apart) for test-retest comparison purposes. We hypothesize that individuals with CUD will exhibit widespread decreases in mGluR5 availability from levels measured during initial abstinence, and that decreases in mGluR5 will be related to blunted activity of cognitive flexibility-related networks and stable or increased activity within automaticity-related networks.

2. Probable Duration of Project:

5 years.

3. Background:

Illicit-substance-use disorders affect over 8% of individuals in the US (1), leading to negative health outcomes and a substantial impact on society (2). Despite decades of research, cocaine use disorder (CUD) remains one of the most treatment-resistant addictions; there is currently no FDA-approved medication with an indication for the treatment of CUD (3), and behavioral interventions for CUD remain suboptimal with high rates of relapse (4).

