Remote screening option. Potential subjects who pass the phone screen portion will have the option to do the consenting screening portion remotely. They will be sent two copies of the consent form and a release of information to review at their leisure through a method that is most convenient for them (i.e., email, fax, or mail). This way subjects have time to review the consent prior to signing and they have their own copy to follow along and ask questions during the consenting phone call. If they agree to participate, subjects can keep one copy of the consent and sign, date, and return the other copy along with a signed release of information back to our research office either by fax, email, or mail in a prepaid envelope. When the consent is also signed by a member of the research team, it will be filed in the subject's research record. Using tele-health platforms (i.e., Zoom) the researcher and subject will thoroughly review and sign the consent form, complete a structured clinical interview (SCID) by a member of the research team, and a medical history and psychiatric interview by a study physician. This will take up to two hours to complete in total. If deemed eligible by initial Zoom call and interviews, potential subjects will be asked to complete the rest of the study procedures as detailed in the protocol.

Consenting individuals will then undergo additional screening evaluation, including a clinical psychiatric interview (including questions regarding patterns/routes of cocaine use) and the collection of other clinical phenotypic information (e.g., body mass index, frequency and amount of cocaine use, comorbid nicotine and alcohol use, etc.) that may be completed in-person or remotely, and an in-person physical examination, including a blood draw for CBC and basic metabolic panel, a pregnancy test if needed, an electrocardiogram, and a urine sample for urinalysis and toxicology tests. Results of these tests are confidential. A qualified physician will inform the subjects of any clinically significant results. Subjects will be asked to complete a release of information form allowing study staff to contact the subject's primary care physician to corroborate aspects of the patient's medical history. If the participant does not have a primary care physician, the release will be completed with another alternative source of collateral information (i.e., parent, relative, or significant other).

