c. PET imaging of mGluR5 with [¹⁸F]FPEB (CUD and HC subjects)

PET scanning sessions will take place at the Yale University PET Center. Subjects will participate in one [¹⁸F]FPEB scan. However, in situations where a PET scan is not successful following [¹⁸F]FPEB injection (e.g., problems with the PET camera), CUD subjects may be rescheduled to complete an additional PET scan, if possible within the 2-5 day window following inpatient admission. HC subjects will complete [¹⁸F]FPEB PET as part of other Yale approved protocols (HIC#1101007933, HIC#1111009365, HIC#2000027842/2000020186).

The PET scan will be acquired as the subject lies supine on the scanner bed. Venous catheters will be used for intravenous administration of the radiotracer and possibly for additional venous blood sampling. A radial artery catheter may be inserted by an experienced physician before the PET scan to draw arterial blood samples for metabolite analysis and for determination of the fraction of plasma radioactivity unbound to protein. Prior to arterial line placement, the skin will be numbed with a local anesthetic so participants will feel less pain when the catheter is inserted. The goal of the arterial line is to be able to measure absolute physiological functions by mathematically relating the signal (from the PET scanner) to the tracer availability (from the blood). This approach is the gold standard for obtaining quantitative PET data. In some cases, for well-established tracers, methods have been developed and validated that provide comparable results to the gold standard. In those cases, the arterial samples may not be necessary. However, validation of such an approach must be performed in each subject group and for each unique experimental design. In this study, if an arterial line cannot be placed, a second intravenous line may be placed for venous blood sampling.

PET scans will be performed with the Siemens HRRT. An attenuation correction scan is obtained immediately before or after each emission scan. The PET scan will be acquired using bolus or bolus plus constant infusion administration of up to 5 mCi of [¹⁸F]FPEB, followed by up to 120 minutes of dynamic PET data acquisition.

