CUD subjects recruited through similar ongoing cocaine studies (e.g., HIC#2000029552) will complete study procedures according to the same timeline. Research-recruited CUD subjects may be discharged from the CNRU according to the procedures and timeline of the referring protocol if additional procedures are to be completed for that study after PET/MRI scanning.

HC subjects recruited through the ongoing [¹⁸F]FPEB PET studies (HIC#1101007933, HIC#1111009365, HIC#2000027842/2000020186) will complete interviews and PET scanning as part of participation in those studies. Any additional interviews (e.g. SSADDA) and all self-assessments will be administered following successful PET scanning. HC subjects will complete MRI procedures within a week of PET scanning, or as near the date of PET scanning as equipment availability allows.

f. Pilot addendum: Second PET and fMRI in early abstinence

A pilot sample of CUD participants (up to 10) will be invited to repeat [¹⁸F]FPEB PET and fMRI procedures within one month of initial scans (typically 10-20 days). Following completion of primary study procedures described above, CUD participants agreeing to complete the optional scanning procedures will remain on the CNRU until the second PET and fMRI procedures can be successfully completed. Participants may also be asked to repeat additional questionnaires and cognitive testing around the time of scanning procedures. While participants are expected to remain on the unit an additional 10-20 days total, rare occurrences in scheduling may require more flexibility and inpatient stays extended up to approximately one month. Given the current scheduling practices at the Yale PET Center and MRRC, participants will likely be provided information regarding the likely dates of additional scans and thus the approximate duration of the extended stay required to complete the pilot study during the consenting processes. HC subjects (up to 10) will be recruited to participate in the fMRI portion of Aim 5. These community-recruited HC individuals will complete screening procedures (that may include remote interviews and consenting), self-assessments and participate in two MRI scanning session up to 30 days apart as scheduling allows.

5. Genetic Testing: N/A

6. Subject Population:

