- *For females:* non-lactating, no longer of child-bearing potential or agreeing to practice effective contraception during the study (e.g., established use of oral, injected or implanted hormonal methods of contraception; placement of an intrauterine device [IUD] or intrauterine system [IUS]; barrier methods: condom or occlusive cap [diaphragm or cervical/vault caps] with spermicidal foam/gel/film/cream/suppository; male partner sterilization; true abstinence when this is in line with the preferred and usual lifestyle of the subject), and a negative serum pregnancy (β -HCG) test

CUD subjects:

- DSM-5 criteria for moderate or severe cocaine-use disorder
- Positive urine toxicology screen for cocaine

CUD subjects (Pilot addendum):

- Successful completion of primary study procedures
- Provide voluntary, written, informed consent to participate in additional procedures

Exclusion criteria:*HC and CUD subjects:*

- Any condition that, in the opinion of investigators, would prevent compliance with the study protocol
- A history of significant medical or neurological illness (e.g., coronary artery disease, significant anemia, seizures)

- Current use of psychotropic and/or potentially psychoactive medications
- Physical or laboratory (β -HCG) evidence of pregnancy
- Meet any additional PET/MR imaging-related exclusion criteria, including:
 - Presence of MRI incompatible implants and other contraindications for MRI (e.g., pacemaker, artificial joints, non-removable body piercings, etc.)
 - Participation in other research studies involving ionizing radiation within one year of the PET scans that would cause the subject to exceed the yearly dose limits for healthy volunteers
 - History of a bleeding disorder or are currently taking anticoagulants (such as Coumadin, Heparin, Pradaxa, Xarelto).
 - Claustrophobia
 - Severe motor problems that prevent the subject from lying still for PET/MR imaging
 - Complaints of chronic pain (e.g., as the result of rheumatoid arthritis)
 - Current, past or anticipated exposure to radiation in the work place

CUD subjects:

- Other moderate or severe drug use disorder (except for tobacco-use disorder)
- < 1 year of cocaine use disorder
- A DSM-5 major psychiatric diagnosis (schizophrenia, bipolar disorder, etc.) unrelated to cocaine

HC subjects:

- Any DSM-5 major psychiatric diagnosis (schizophrenia, bipolar disorder, etc.), except tobacco-use disorder
- Positive drug screen

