participate in the fMRI portion of this study. Additional HC subjects will be recruited through the community. Subjects will undergo a process of informed consent in person or remotely, including reading the consent form and reviewing it with a research staff member. Subjects will receive an explanation of purpose, procedures, benefits, risks, compensation, and alternatives to the study. They will have time to ask any questions and, if interested in participating, will be asked to sign an approved consent form. Subjects from other [¹⁸F]FPEB PET studies may be asked to undergo a structured interview (i.e., SCID) to confirm eligibility if this or a comparable assessment was not completed by the referring study.

10. Risks:

a. Risks associated with interviews, questionnaires and neurocognitive testing

The medical and psychiatric interviews, self-report questionnaires, and computerized neurocognitive tests may be stressful, uncomfortable, or tiring for subjects. Unanticipated psychiatric and medical information may be uncovered during evaluation.

b. Risks associated with phlebotomy/intravenous lines

Drawing blood and inserting an intravenous line (IV) are safe and standard medical procedures. Venous sampling may be associated with mild-to-moderate pain or bruising at the puncture site. Bruising and thrombosis can occur during phlebotomy and the placement of the intravenous line. In rare instances poor healing, or infection at the catheter insertion site may occur. Certain individuals may feel light-headed during venipuncture; to avoid injury due to fainting, procedures will be performed when the subjects are seated/recumbent. Blood samples will be drawn for routine labs (up to 60mL) and blood will be taken during each PET scan (up to 120mL).

c. Risks associated with use of an arterial catheter

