On the PET scanning days a radial arterial catheter may be inserted. Certain individuals may feel light-headed during arterial catheter placement. Arterial catheter placement may be associated with mild-to-moderate pain, hematoma, inflammation, bleeding, or bruising at the puncture site. If any of these, or other, symptoms occur and do not diminish within 24 to 72 hours after the arterial line removal, or in the event that they worsen, subjects will be advised to call the on-call doctor listed on the PET discharge instructions. In rare instances blocking of the artery, tearing of the artery, arterial leakage, poor healing, or infection at the catheter insertion site may occur.

d. Risks associated with MRI

Functional MRI scanning using a 3.0T scanner is non-invasive and has not been associated with any medical risks. However, MRI scanning carries a risk for subjects who are claustrophobic or have pacemakers, metal pieces, aneurysm clips, or any other contraindications for MR. As individuals with contraindications for MR will be excluded, the primary anticipated complication is the experience of claustrophobia during scanning. On rare occasions, some people might feel dizzy, get an upset stomach, have a metallic taste or feel tingling sensations or muscle twitches. Another risk is the possibility of metal objects being pulled into the magnet and striking the subject or heating up during scanning. While the scans performed in this study are not designed for diagnostic purposes, potential abnormalities may be detected by the MR technologist during acquisition, or members of the research team during image analysis.

e. Risks associated with radiation

This research study involves exposure to radiation from [¹⁸F]FPEB PET scanning. This radiation exposure is not necessary for medical care and is for research purposes only. The targeted amount of radiation an

individual subject will receive from participating in Aim 1 of this study is from one injection of \leq 5mCi (0.57 rem) of [¹⁸F]FPEB, plus attenuation correction (i.e., transmission) scans of the brain. Participants that return to complete a second PET scan as part of Aim 5 will receive a second injection of \leq 5mCi (0.57 rem) of [¹⁸F]FPEB, for a total of 1.14 rem.

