b. Minimizing risks from phlebotomy/intravenous lines

The risks of bruising, clotting, and infection will be minimized by having venipuncture performed by trained and experienced personnel using aseptic technique. To avoid injury due to fainting, the intravenous catheters will be inserted when the subjects are recumbent. Subjects completing study procedures will have no more than 240mL of blood drawn across study participation (including screening, admission and PET scan), which is less than a standard blood donation (450 mL or roughly a pint). To minimize the risks of blood draws

and the discomfort associated with it, there will only be one blood draw on the screening visit and blood draws during PET scanning sessions will be obtained from an inserted catheter. Subjects with history of significant anemia will be excluded, and subjects will be asked to abstain from using aspirin, NSAIDS or anticoagulants unless medically necessary (at which point they will be re-assessed for eligibility). Bleeding is minimized by local pressure applied for 5 minutes after the procedure. Infection is avoided by adequate cleansing of the skin prior to venipuncture and by the exclusion of immunocompromised subjects.

c. Minimizing risks from an arterial catheter

Risks of radial artery cannulation are minimized by having the procedure performed by an experienced health care provider. The health care provider would be either a physician or an advanced practice registered nurse (APRN) with experience in critical care and placement of arterial catheters, as is the practice at Yale-New Haven Hospital. For an APRN to place the arterial line at the Yale PET Center, they must meet the following criteria:

- 1.) Be currently credentialed at Yale-New Haven Hospital or similar institute and
- 2.) Perform 3 arterial line procedures supervised by a currently privileged PET Center physician

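### The 240 mL blood limit fits a one-scan subject, but the stated per-procedure maxima do not guarantee it once a second or third PET scan is done

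*Combined protocol and SAP*

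**What the plan says.** Four parts of the protocol bear on the total blood volume.

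- **Overall limit.** Section I, 11.b (minimizing risks from phlebotomy and intravenous lines) states "no more than 240mL of blood drawn across study participation (including screening, admission and PET scan"), and compares this with a 450 mL blood donation.
- **Volumes by procedure.** Section I, 10.b (the matching risk section) gives "routine labs (up to 60mL) and blood will be taken during each PET scan (up to 120mL"). Section I, 4.b makes a screening draw part of the evaluation: "including a blood draw for CBC and basic metabolic panel".
- **Number of scans.** Section I, 4.c plans one scan for the main study, but after a failed scan "CUD subjects may be rescheduled to complete an additional PET scan, if possible within the 2-5 day window following inpatient admission". Section I, 4.f adds the pilot addendum: "A pilot sample of CUD participants (up to 10) will be invited to repeat" the PET and fMRI procedures. Section I, 10.e confirms the extra scan: "Participants that return to complete a second PET scan as part of Aim 5 will receive a second injection". It also allows up to three injections for an Aim 5 subject when a scan has failed.
- **Whether PET blood is taken.** Section I, 4.c makes an arterial line and extra venous sampling possible, not certain.

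**The concern.** The limit is worded to cover the whole of a subject's participation, while the PET volume is set per scan and the design allows one, two or three scans. Section I, 10.e builds the radiation dose up by number of scans (0.57, 1.14 and 1.71 rem). Nothing similar is done for blood, and 11.b mentions the PET scan in the singular. This looks like a figure set for one scan and not revisited for the repeat scans.

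What is at stake is a numerical subject-protection limit in a study that the protocol rates as greater than minimal risk. Staff could stay within 10.b at every scan and still exceed 11.b. Power, estimates and analyses are not affected.

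**Working it through.** **Inputs.** Labs: up to 60 mL (10.b). PET: up to 120 mL per scan (10.b). Limit: 240 mL (11.b). Comparator: 450 mL (11.b). Scans: one for Aim 1 (4.c), two for Aim 5 or a repeated Aim 1 scan (4.c, 4.f), three for Aim 5 with one failed scan (10.e).

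**Formula.** Maximum total = labs + 120 × number of scans.

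**Reproducing 240 mL.** The protocol does not show how the figure was built. If the 60 mL of labs is drawn at both screening and admission, 60 + 60 + 120 = 240 mL for one scan, exactly the stated limit. That split is an assumption, though it matches the three items listed in 11.b. With labs counted once, one scan gives 180 mL. Either way the limit holds for one scan.

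**All cases.**

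| Scans | Labs 60 mL in total | Against 240 mL | Labs 60 mL at each of screening and admission | Against 240 mL |
|---|---|---|---|---|
| 1 | 60 + 120 = 180 | 60 under | 120 + 120 = 240 | at the limit |
| 2 | 60 + 240 = 300 | 60 over (60/240 = 25%) | 120 + 240 = 360 | 120 over |
| 3 | 60 + 360 = 420 | 180 over | 120 + 360 = 480 | 240 over |

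Only the last cell, 480 mL, passes the 450 mL comparator.

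**Does the excess depend on the lab figure?** Not in kind. Two fully sampled scans use 2 × 120 = 240 mL, which leaves nothing for the screening draw.

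**Sampling that would keep to 240 mL.** With 60 mL of labs and two scans: (240 − 60)/2 = 90 mL per scan, or 90/120 = 75% of the stated maximum. If the first scan has already taken 120 mL, 240 − 60 − 120 = 60 mL remains for the second. With three scans: (240 − 60)/3 = 60 mL per scan. With 120 mL of labs, the figures are (240 − 120)/2 = 60 mL per scan for two scans and (240 − 120)/3 = 40 mL for three.

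**The case against.** The strongest reply is that ceilings for single procedures may add up to more than an overall cap, and the cap then governs. The wording of 11.b is ordinary cap wording, and the protocol performs no sum that comes out wrong. This part stands: the point is an internal inconsistency, not a miscalculation. But no section says which limit prevails, asks for a running total, or reduces sampling at a later scan.

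A second reply is that 240 mL covers only the main study. The singular PET scan in 11.b supports this, as does the reproduction of 240 mL from one scan, and addendum subjects must give "informed consent to participate in additional procedures" (Section I, 8). Against it, the limit is said to apply across study participation, and 11.b does not use the label for the main-study procedures that the protocol uses in 4.f, in item 8 and in the payment table of Section VI. That table also lists the addendum payments under the same consent group as the main study. The reading is possible but not written. It would in any case leave two- and three-scan subjects with no stated total, and it does not cover a repeated Aim 1 scan.

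A third reply, that 120 mL is a total over all scans, conflicts with the per-scan wording of 10.b.

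A reader might go further and infer that the limit will be breached, or that unsafe volumes are planned. The documents support neither. The volumes are upper bounds, PET blood sampling is conditional, no expected volume is given, and a failed scan may end before full sampling.

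**Conclusion.** The point holds as a minor internal inconsistency. The 240 mL limit is consistent with one scan, but the stated maxima do not guarantee it beyond that: 300 mL for a planned Aim 5 subject or a repeated Aim 1 scan, and 420 mL for three scans. With labs at 60 mL, a two-scan subject exceeds the limit only if PET sampling averages more than 90 mL per scan. The planned two-scan group is at most 10 of the 20 CUD subjects; repeats of failed scans would add to it.

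The 300 and 420 mL figures assume that 60 mL covers screening and admission labs together. If 60 mL is drawn at each, they become 360 and 480 mL, and the last would also undo the comparison with a 450 mL donation. Sample size, schedule and analysis are unaffected.

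**What to change.** First establish how 240 mL was built, in particular whether the 60 mL of labs covers screening and admission together. Then change 11.b in one of two ways; the choice is for the investigators.

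1. **Restrict and extend.** Limit the 240 mL statement to one-scan main-study participation, and state maxima of 300 mL for two scans and 420 mL for three (360 and 480 mL if labs are drawn twice, in which case the donation comparison must be reworded for three scans). The cost is wording only, with a less favourable stated maximum.
2. **Binding cap.** State that 240 mL is cumulative and includes the addendum and any repeat scan. Keep a running total for each subject and limit PET sampling to what remains: for example, at most 90 mL per scan when two are planned and labs use 60 mL. An unplanned third scan would have only the remainder. The cost is less blood per scan. The protocol does not say what volume the metabolite and plasma-fraction analyses need, so the PET team must confirm that the reduced volume is sufficient.

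Under either option, check that the consent text, which was not available for this review, gives the same figure.
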